5.5. STATISTICAL TESTS

No formal statistical hypotheses will be tested in this study.

Two-sided 95% confidence intervals will be calculated and two-sided, unless otherwise specified in the description of the analyses.

5.6. COMMON CALCULATIONS

For quantitative measurements, change from baseline will be calculated as:

Test Value at Visit X – Baseline Value

5.7. SOFTWARE VERSION

All analyses will be conducted with SAS version 9.4 or higher based on Enterprise Guide version 7.1.

6. STATISTICAL CONSIDERATIONS

6.1. ADJUSTMENTS FOR COVARIATES AND FACTORS TO BE INCLUDED IN ANALYSES

No adjustment will be performed.

Document: [REDACTED]

Author: [REDACTED] Version Number: 2.5

Version Date: 18Feb2022

Template No.: [REDACTED] Reference: CS_WI_BS005

Effective Date: 02Dec2019

6.2. MULTICENTER STUDIES

This study is planned to be carried out at up to 10 sites. However, no adjustment in aspect of site effect will be performed. Data from all centers will be pooled for the analysis.

6.3. MISSING DATA

Generally, the missing efficacy and safety data will not be imputed except for the critical missing and partial dates which will be handled as described in this section. In the situation where partial or missing date are imputed, the date will appear partial or missing in the listings, while imputed date will only be used for calculation.

6.3.1. MISSING DATES INFORMATION OF STUDY TREATMENT

When the date of the last dose of study treatment is missing for a patient, all efforts should be made to obtain the date from the investigator. If it is still missing after all efforts, the last dose date collected from the [Study Drug Administration] page of or data cut-off date (if applicable) will be used in the calculation of treatment duration.

6.3.2. MISSING OR INCOMPLETE DATE INFORMATION FOR ADVERSE EVENT DATE

For the purpose of determining whether an adverse event (AE) is treatment emergent (see [section 17.2.1](#)), incomplete start dates and/or stop dates will be imputed. Start date will be imputed first when the start date and stop date are both incomplete for a patient. If the field of year is missing or start date of an AE is completely missing, then no value will be imputed. The following rules will be applied to impute the incomplete start date, assuming year is available.

Missing or incomplete start date

- In case the start date of an AE is in the same year as reference start date (when only year is recorded), or the start date is in the same month and year (if only the day is missing) as the reference start date, then the start date of the AE will be imputed by the reference start date or the AE resolution date, whichever occurs earlier.
- If the day and month parts of the AE onset date are missing and occur in the same year as the first dose of study drug, the date of the first dose of study drug will be used as the onset date of the AE. If an AE is observed on different year of first dose, January 1st will be used to complete the onset date of the AE.
- If only the day part of the AE onset date is missing and occurs in the same month and year as the first dose date of study drug, the date of first dose of study drug will be used as the onset date of the AE. Otherwise, the first day of the month will be used to complete the onset date of the AE.
- In all other cases, imputation will not be performed.

Here are some examples.

Incomplete Date of Onset (DD MMM YYYY)	Reference Start Date (DD MMM YYYY)	Imputed Date (DD MMM YYYY)
-----	10Apr2017	-----

Document: [REDACTED]

Author: [REDACTED] Version Number: 2.5
Version Date: 18Feb2022

Template No.: [REDACTED] Reference: CS_WI_BS005

Effective Date: 02Dec2019

Incomplete Date of Onset (DD MMM YYYY)	Reference Start Date (DD MMM YYYY)	Imputed Date (DD MMM YYYY)
----2017	10Apr2017	10Apr2017
----2018	10Apr2017	01Jan2018 (because the AE onsets after the reference date)
--Apr2017	10Apr2017	10Apr2017
--Oct2017	10Apr2017	01Oct2017
05---2017	10Apr2017	05---2017

Missing or incomplete stop date

Incomplete stop dates will be imputed to the last possible date:

- If the known part(s) of the AE end date is (are) the same as the death date/ end of study date, the AE end date will be imputed by the death date/ end of study date, whichever occurs earlier.
- In all other cases, the AE end date will be imputed to the last day of the month if only the day is missing or imputed to with 31st December if both day and month are missing.
- If the imputed stop date is before the start date (imputed or non-imputed start date), then the stop date will be imputed using start date.
- If the end date is completely missing or the year part is unknown, the end date will not be imputed.

Here are some examples:

Incomplete AE End Date (DD MMM YYYY)	Date of Death/ End of Study (DD MMM YYYY)	Imputed Date (DD MMM YYYY)
--May2017	Not Available/ Not Available	31May2017
--Sep2017 (known part the SAME as date of death/ end of study)	-----/ 09Sep2017	09Sep2017
----2017 (known part the SAME as date of death/ end of study)	09Sep2017/ 09Sep2017	09Sep2017
--Jun2017 (known part DIFFERENT from date of death/ end of study)	09Sep2017/ 09Sep2017	30Jun2017
-----	-----/ 09Sep2017	-----
31Dec----	09Sep2017/ 09Sep2017	31Dec----
----2018	09Oct2019/ 09Oct2019	31Dec2018

Document: [REDACTED]

Author: [REDACTED]

Version Number:

2.5

Version Date:

18Feb2022

Template No.: [REDACTED]

Reference: CS_WI_BS005

Effective Date: 02Dec2019

6.3.3. MISSING OR INCOMPLETE DATE INFORMATION FOR CONCOMITANT MEDICATION/ PROCEDURE

The imputation rule is the same as described for adverse event.

6.3.4. MISSING OR INCOMPLETE DATE INFORMATION FOR PRIMARY DIAGNOSIS DATE AND METASTATIC DIAGNOSIS DATE

Imputation will only be applied in case the field of year is available. If year and month are known but the day is unknown, day will be imputed as 15. If only year is known, month and day will be imputed to July 1st. If the diagnosis date is completely missing or the year part is unknown, the diagnosis date will not be imputed.

6.3.5. MISSING OR INCOMPLETE DATE INFORMATION FOR EFFICACY DATA

When a partial new anticancer therapy starting date is reported, every effort will be made to identify the precedence relationship of starting date of new anticancer therapy relative to last dosing date of study drug and the date of disease progression (if happened). According to the confirmed precedence relationship, partial new anticancer therapy date will be imputed to the earliest possible date:

- Day will be imputed as 1 if year and month are known; month and day will be imputed as Jan 1st if only year is known.
- In rare case, if year and month of death date are known but the day is unknown, day will be imputed as 15. For example, if a patient is reported to die on Dec2017, the death date will be imputed as 15 Dec2017.

However, the imputed anticancer start date will be adjusted based on corresponding date in different scenario as shown below, the imputed date will be set to the date according to which it will be adjusted if the originally imputed date is earlier than the corresponding date:

- Adjust based on the date of first dose in case that anticancer therapy starts earlier than both last dosing date and disease progression.
- Adjust based on the last dosing date/the date of disease progression which occurs earlier in case that anticancer therapy is initiated after last dosing date but before disease progression date or vice versa.
- Adjust based on the last dosing date/the date of disease progression which occurs later in case that anticancer therapy is initiated after both last dosing and disease progression.

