16.1.6. OVERALL SURVIVAL (OS)

The OS (in months) refers to the time interval between the first dose date and the date of death (any cause). The last known alive date (i.e. the last follow-up date in patients on study or the date of EOS in patients withdrawn from the study) will be used as the censoring date for patients who have not died at the time of the statistical analysis. Patients lacking data beyond the first dose date will have their survival time censored at the first dose date.

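### SAP 6.3.5 sets an unknown day of death to the 15th without checking it against later dates on which the patient was known to be alive

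*SAP*

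**What the plan says.** SAP 6.3.5 gives one rule for a partial death date: "if year and month of death date are known but the day is unknown, day will be imputed as 15". Its example is that "if a patient is reported to die on Dec2017, the death date will be imputed as 15 Dec2017". The adjustment bullets that follow open with "However, the imputed anticancer start date will be adjusted based on corresponding date in different scenario as shown below", so they govern the start of new anticancer therapy and not death.

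SAP 6.3 says of imputed dates in general that the "imputed date will only be used for calculation", so the imputed death date enters the derivations. SAP 16.1.6 measures OS from first dose to death. It defines a last known alive date, but that date "will be used as the censoring date for patients who have not died at the time of the statistical analysis"; it is not a lower bound for patients who have died.

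Elsewhere the SAP does guard against impossible sequences. In SAP 6.3.2, if an imputed adverse-event stop date falls before the start date, "then the stop date will be imputed using start date". The protocol has no rule for partial death dates.

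**The concern.** A fixed day 15 ignores information already in the database. A patient who took a dose, had a scan or answered a call on the 20th, and whose death is recorded only by that month, would be analysed as having died on the 15th.

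The death date is used in several places:

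- **OS** (SAP 16.1.6): it is the event date.
- **Exposure** (SAP 15.3): for patients off treatment, total duration stops at death if that comes before last dose plus 8 days. A death dated before the last dose shortens the denominator of dose intensity.
- **On-study death** (SAP 17.3): the flag covers deaths after first dose and up to 37 days after last dose. A date that is too early can fall before first dose, or be pulled back inside the 37 days.
- **Adverse-event end dates** (SAP 6.3.2): a partial end date whose known parts match the death date can be set to it.
- **PFS** (SAP 16.1.5, Table 1): death without earlier progression is an event on the date of death.

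**Working it through.** **Inputs.** The day-15 rule is from SAP 6.3.5. Landmark weeks 12, 16, 20 and 24 are from SAP 16.2. Cohort sizes of 40 (B and C) and 15 (D and E) are from protocol 8.6. The documents do not give the number of partial death dates or the gap between last contact and death, so the gap is shown as a range.

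**1. The SAP's own example.** A death reported as December 2017 becomes 15 December 2017 whatever else is recorded for the patient. This reproduces the SAP figure.

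**2. Error of the imputed date.** Error = 15 − true day.

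| Month length | Earliest error | Latest error |
|---|---|---|
| 31 days | 15 − 31 = −16 | 15 − 1 = +14 |
| 30 days | 15 − 30 = −15 | +14 |
| 28 days | 15 − 28 = −13 | +14 |

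With all days of a 31-day month equally likely, the mean true day is (1 + 31)/2 = 16 and the mean error is 15 − 16 = −1 day. The rule is close to centred when nothing else is known. The trouble is confined to patients with evidence of life after the 15th. For them the true day is 16 or later, so the error can only be early.

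**3. How often the sequence is impossible.** Assume a 31-day month, a uniform day of death d, and last contact g days before death. The imputed death precedes last contact when d − g > 15.

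| Gap g (days) | Days d affected | Share |
|---|---|---|
| 0 | 16 to 31 | 16/31 = 52% |
| 7 | 23 to 31 | 9/31 = 29% |
| 14 | 30 and 31 | 2/31 = 6% |
| 16 or more | none | 0% |

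These shares apply to deaths with an unknown day, not to all deaths.

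**4. Negative survival.** First dose on the 20th and death later in that month: 15 − 20 = −5 days.

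**5. Crossing a landmark (assumed dates).** First dose 30 September 2020, contact 28 December 2020, death recorded as December 2020.

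- Current rule: death on 15 December, 76 days after first dose, study day 77, before week 12 (84 days).
- With a floor: death on 28 December, 89 days after first dose, study day 90, after week 12.

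If that death is the PFS event, the patient changes from failure to event-free at week 12. Ignoring censoring, one patient is worth 1/40 = 2.5 points or 1/15 = 6.7 points. For scale, 20/40 = 50.0% (Clopper-Pearson 95% CI 34 to 66, as in protocol Table 16) becomes 19/40 = 47.5% (32 to 64).

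**The case against.** The case for leaving the rule alone is that the problem needs several unlikely things together. Protocol 7.1.8.5 has deaths either reported immediately or recorded on the end-of-treatment and end-of-study forms. Note 17 to protocol Appendix A asks for the date and cause of death during survival follow-up, and protocol 12 has discrepant data queried. An unknown day is most plausible for deaths learned of at the 12-weekly telephone call. Last contact is then often more than 16 days before death, and no inversion is possible. The 52% figure assumes contact on the day of death, when the day would normally be known. All of this stands and limits the size.

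Four stronger readings are tempting, and the documents do not support them:

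- A reader might infer that death is the only imputed date without a bound. SAP 6.3.4 also imputes diagnosis dates (day 15, or 1 July) without one, although these feed only baseline durations.
- A reader might infer that the rule always dates death too early. The error runs from −16 to +14 days, and only the inversions are one-directional. The 15th can even fall after a data cut-off earlier in the month.
- A reader might infer that the PFS rates are distorted generally. Table 1 uses death as the event only without earlier progression, prior new therapy or two missed assessments, and a landmark must also lie inside the shift. Protocol 8.6 already puts the confidence limits at about ±7 to 16 points (n=40) and ±16 to 28 points (n=15), and SAP 5.5 plans no hypothesis test.
- A reader might infer that adverse-event end dates are broadly affected. The death date is used only when the known parts match, and the result is still floored at the start date.

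None of this supplies the missing check.

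**Conclusion.** The point holds as a minor defect in a stated rule. As written, SAP 6.3.5 can date a death before a recorded dose, visit, scan or contact, and even before first dose. The shift in such a patient is 1 to 16 days early in a 31-day month.

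OS is affected in every such case. Exposure duration, the on-study-death flag and imputed adverse-event end dates are affected when the shifted date crosses the limits that those derivations use. A PFS rate changes, by about 2.5 points at n=40 or 6.7 points at n=15 per patient, only when death is taken as the PFS event and a landmark week falls between the imputed and true dates.

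The 16-day limit follows from the calendar. The frequencies rest on an assumed uniform day of death and an assumed contact gap. Neither document shows how many patients are affected, and the SAP expects few.

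**What to change.** Add a sentence to SAP 6.3.5 before database lock: when only the day of death is unknown, impute the later of the 15th and the last observed date on which the patient was known to be alive (first or last dose, visit, scan or contact), capped at the earlier of month end and data cut-off.

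Two details matter. The floor must use observed dates only, because SAP 6.3.1 allows a missing last-dose date to be replaced by the data cut-off, and using that as a floor could push a death too late. The cut-off cap removes the late-side impossibility as well.

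The cost is small. SAP 16.1.6 applies a last known alive date only to patients who have not died, so the same derivation must be extended to deceased patients with a partial death date. Cases with no evidence of life after the 15th, and no cut-off before it, keep the present value.

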6.4. MULTIPLE COMPARISONS/ MULTIPLICITY

There are no requirements for multiplicity adjustments in this study.

6.5. EXAMINATION OF SUBGROUPS

No subgroup analyses will be performed for this study.

Document: [REDACTED]

Author: [REDACTED] Version Number: 2.5

Version Date: 18Feb2022

Template No.: [REDACTED] Reference: CS_WI_BS005

Effective Date: 02Dec2019

7. OUTPUT PRESENTATIONS

[Appendix 2](#) shows conventions for presentation of data in outputs.

Format and content of summary tables, figures, and listings are presented as mock shells for TFLs and provided by IQVIA Biostatistics.

Continuous variables will be summarized using descriptive statistics including, number of patients (n), mean, median, standard deviation (STD), 25% and 75% quantiles, minimum and maximum. Categorical variables will be summarized with number and percentage and presented in frequency tables. All results will be presented by dose cohort (only in dose escalation phase) or tumor specific cohorts (only in dose expansion phase).

Qualitative variables will be summarized by count(s) and percentages (%).

Percentages will be reported with 1 decimal point; if the count is 0, no percentage will be presented. Value of percentage less than 1% will be presented as “<1%.” Value of percentage less than 100% but >99% will be presented as “>99%.” Any rounding will be done after all calculations are made.

8. DISPOSITION AND WITHDRAWALS

8.1. ENROLLMENT

Information of all patients who provided informed consent (that is the ENR) will be included in the summary of disposition and withdrawals for this study. A summary table will be generated to provide the following:

- Number of patients who signed the informed consent
- Number of screen failures
- Reason for screen failure
- Number of patients who passed screening
- Number of patients who withdrew consent before study treatment
- Number of patients who received treatment

A separate table will be presented to show the patients included in each analysis set and reason for exclusion from an analysis set.

Document: 

Author: 

Version Number:

2.5

Version Date:

18Feb2022

Template No.: 

Reference: CS_WI_BS005

Effective Date: 02Dec2019

8.2. PATIENT STATUS AT TREATMENT AND STUDY COMPLETION

Patient status at treatment and study completion will be listed and summarized for SAS. The listing will include individual information (i.e. site and patient number, informed consent information), whether patients discontinued from the treatment and the reasons for the discontinuation, along with the date of first/ last dose, duration of treatment, and the date of discontinuation from the treatment. The same information will be provided for patients who discontinued from the study. The following summaries will be presented:

- Patients still on treatment
- Reason for study drug discontinuation (for study drug)
- Number of patients going into Survival follow-up
- Number and percentage of patients who discontinue the study
- Reason for study discontinuation

A flowchart for disposition will be presented.

9. PROTOCOL DEVIATION

Protocol deviations are recorded as critical, major or minor in Clinical Trial Management System (CTMS) and are classified into 10 categories:

- Administrative Criteria
- Eligibility and Entry Criteria
- Informed Consent Criteria
- IP Compliance
- Laboratory Assessment Criteria
- Regulatory or Ethics Approvals Criteria
- Serious Adverse Event Criteria
- Study Procedures Criteria
- Visit Schedule Criteria
- Other Criteria

Major protocol deviations are those recorded as critical or major.

All subject-level protocol deviations will be presented in listing including deviation date and severity.

Document: [REDACTED]

Author: [REDACTED]

Version Number:

2.5

Version Date:

18Feb2022

Template No.: [REDACTED]

Reference: CS_WI_BS005

Effective Date: 02Dec2019

10. DEMOGRAPHIC AND OTHER BASELINE CHARACTERISTICS

Demographic data and other baseline characteristics will be presented for the SAS. Data listing will also be provided.

No statistical testing will be carried out for demographic or other baseline characteristics.

The following demographic and other baseline characteristics will be reported for this study:

- Age (years) – calculated relative to date of consent; summarized as both continuous variable and categorical variable (< 65 vs. ≥ 65 years)
- Gender
- Race
- Ethnicity
- Weight (kg)
- Height (cm)
- BMI (kg/m²): summarized as both continuous and categorical variable (<18.5, ≥18.5 and <24, ≥24 kg/m²)
- Baseline ECOG performance status (0, 1, 2, 3, 4, 5)

10.1. DERIVATIONS

BMI (kg/ m²) = weight (kg)/ height (m)²

11. SURGICAL AND MEDICAL HISTORY

Medical and surgical history will be coded by MedDRA Version 23.1 or higher and summarized separately for SAS; results will be expressed by system organ class (SOC) and preferred term (PT) in descending order of the frequency in total. For SOCs or PTs with the same frequency, results will be sorted alphabetically.

Individual patient listings of and medical/surgical history will also be provided for the SAS.

12. ONCOLOGY HISTORY

Oncology history information will be presented for the SAS. The following oncology history information will be summarized:

Document: [REDACTED]

Author: [REDACTED] Version Number: 2.5
 Version Date: 18Feb2022

Template No.: [REDACTED] Reference: CS_WI_BS005

Effective Date: 02Dec2019

- Primary diagnosis of malignancy
- Time since primary diagnosis to first dose of study treatment (months)
- Primary site
- Diagnosis of malignancy at enrollment
- Metastatic status (yes, no)
- Number of metastatic sites: both continuous variable and categorical variable (0, 1, 2, >=3)
- Time since first metastasis diagnosis to first dose of study treatment (months)
- TNM stage at enrollment
- Disease stage at enrollment
- Histological classification at enrollment (Adenocarcinoma, Adenosquamous Carcinoma, Carcinoid, Clear Cell Carcinoma, Indeterminate, Sarcoma, Squamous (except squamous non-small cell lung cancer [NSCLC], Other)
- Prior use of VEGF-R inhibitor (yes, no)
- Prior use of VEGF inhibitor (yes, no)
- Time since last systemic anti-neoplastic therapies to first dose of study treatment (months)
- Liver metastasis (yes, no): obtained based on whether the liver organ was involved in the target and non-target lesion tumor scan assessment at the baseline.

12.1. DERIVATIONS

- Time since primary diagnosis to first dose of study treatment (months) = (Date of first dose of study treatment – Date of primary diagnosis)/ 30.4375
- Time since first metastasis diagnosis to first dose date (months) = (Date of first dose of study treatment – Date of first metastasis diagnosis)/ 30.4375
- Time since last systemic anti-neoplastic therapies to first dose of study treatment (months) = (Date of first dose of study treatment – Date of last systemic anti-neoplastic therapies)/ 30.4375

13. ONCOLOGICAL THERAPIES

13.1. PRIOR ONCOLOGICAL THERAPY

Prior oncological therapy information are recorded as following: Prior oncology medication information, Prior oncology radiotherapy information, Prior oncology surgery and procedure information.

Prior oncology medication will be coded using World Health Organization Drug Dictionary Enhanced (WHO DDE) Version SEP2020. Prior oncology surgery and procedures will be coded using MedDRA Version 23.1 or higher.

Document: [REDACTED]

Author: [REDACTED]

Version Number:

2.5

Version Date:

18Feb2022

Template No.: [REDACTED]

Reference: CS_WI_BS005

Effective Date: 02Dec2019

Prior oncology medications will be presented by Anatomical Therapeutic Classification (ATC)-2nd-level term (ATC level 2) and by PTs for each dose and/ or disease cohort in each phase. ATC class and PT will be sorted in descending frequency of the total number of patients with at least one condition in the corresponding category; ATCs/PTs will be presented alphabetically for ATCs/PTs of the same total frequency. In addition, number and percent of patients who have received prior oncology medication, regimen number, and category of regimen number will be summarized for prior oncology medication.

Prior oncology surgery and procedures will be presented by SOC and PT for each cohort in each phase. SOC and PT will be sorted in descending frequency of the total number of patients with at least one condition in the corresponding category, SOC/PTs will be presented alphabetically for SOC/PTs of the same total frequency. Corresponding listings will be provided.

